## I. BACKGROUND AND SIGNIFICANCE

Waterbirth is a method of pain control during childbirth that has been growing in popularity since the 1970s. The safety of first stage water immersion is well established and is considered an effective method of pain control. Waterbirth advocates claim that it is a low-intervention, physiologic means of pain control for laboring women. The American College of Nurse-Midwives (ACNM) position statement supports the safety of waterbirths attended by qualified maternity providers, yet the 2016 statement by American College of Obstetricians and Gynecologists (ACOG) and endorsed by the American Academy of Pediatrics (AAP) recommended that all waterbirths in the United States be conducted in the context of a clinical trial.

In 2019, ACOG updated Committee Opinion Number 766, *Approaches to Limit Interventions During Labor and Birth*, recommending that clinicians be familiar with approaches to limit unnecessary interventions in labor and birth for low-risk women. While not addressed in the committee opinion, waterbirth may be a less interventive option for pain control compared to standard interventions (e.g. IV narcotics, epidural anesthesia). A literature search was conducted using OVID Medline, CINAHL, PsycInfo, Alt Health watch, Scopus, Embase, Google Scholar, and reference lists of each article. Current literature associates waterbirth with high levels of maternal satisfaction and increased perception of control. It is also associated with a shorter duration of labor. Waterbirth is also associated with increased cases of intact perineum, low likelihood of episiotomy, increased buoyancy, mobility, and maternal upright position, as well as decreased blood pressure. Only five randomized control trials have been conducted and published. In the recently updated Cochrane Database of Systematic Reviews *Immersion in Water During Labor and Birth*, four RCTs of water immersion for both first and second stage labor were included and two studies were of immersion in the second stage of labor only. The trials were conducted in Iran, China, the United Kingdom, and South Africa; and of these, only three are available in English. Results from the trials are available in a secondary source. There have been no RCTs of waterbirth conducted in the United States (USA) and to our knowledge, there are no ongoing trials of waterbirth.

Large retrospective, prospective, and observational trials have also been conducted, mostly outside of the United States. These studies report measurable clinical markers: **maternal markers** include rate of spontaneous vaginal birth (SVD), rate of cesarean section, length of labor, blood loss, use of pharmacological or anesthetic analgesia, and perineal lacerations; **neonatal markers** include Apgar score, admission to neonatal intensive care (NICU), respiratory distress, and rate of infection. The most controversial aspect of waterbirth is the unknown risks and/or benefits to the neonate. Several studies and meta-analyses have focused entirely on neonatal outcomes. One systematic review and meta-analysis included only data from hospital births and found no increased risk to the neonate; however, there is significant heterogeneity among the included studies.

Despite the current body of literature, there are many limitations to use of the above studies in the United States. The authors of the Cochrane review note that studies are not comparable and there were wide protocol and data collection variations. Moreover, the studies come from a wide

variety of countries and health systems, which limits their generalizability and applicability in the United States. Researchers estimate that approximately 6-15% of US hospitals offer waterbirth.

Per ACOG Committee Opinion Number 766, obstetric providers should be familiar with and consider using measures to decrease labor interventions, waterbirth may be one such option with the additional benefit of increasing maternal satisfaction. The 2014 ACNM statement on waterbirth supports waterbirth as an option for low-risk women because it “provides comfort, supports relaxation, and is a safe and effective non-pharmacologic pain relief strategy that promotes physiologic childbirth”. The Cochrane database recommends that waterbirth trials be conducted in midwife-led settings. While our hospital has a multiple types of maternity care providers, we also house the largest group of Certified Nurse Midwives in Wisconsin, making our site ideal for this trial. Moreover, given hospital location, we will offer study participation to a diverse group of low-risk, healthy women with a term pregnancy planning to give birth in the hospital setting. Therefore, we aim to pilot the first randomized control trial for waterbirths in the United States, in order to (1) assess the feasibility of conducting a larger, multi-site trial, (2) explore or test differences in maternal/neonatal outcomes, and (3) explore or test differences in patient satisfaction.

## II. SPECIFIC AIMS

The proposed pilot randomized control trial will be approached as a feasibility study to explore or test (if sample size permits) our hypotheses. Additional sample size analyses have been conducted since this study was first submitted as we continue to explore the feasibility of this study in hopes of answering our primary outcome.

**Primary outcome:** Women in the waterbirth group will use less IV narcotic and epidural anesthesia than women in the land birth group.

We further seek to address the following additional specific aims:

**Specific Aim 1:** Evaluate waterbirth outcomes in adult low-risk laboring women randomized to waterbirth in comparison to women randomized to birth on land.

**Hypothesis 1a.** Women in the waterbirth cohort will have shorter labor duration than women in the land cohort.

**Hypothesis 1b.** Women in the waterbirth cohort will be more likely to initiate breastfeeding before discharge.

**Specific Aim 2:** Evaluate the safety of waterbirth in adult low-risk laboring women randomized to waterbirth in comparison to women randomized to birth on land.

**Hypothesis 2a.** Women in the waterbirth cohort will not experience more adverse outcomes (e.g., postpartum hemorrhage, third- or fourth-degree perineal lacerations, etc.) than women in the control group.

**Specific Aim 3:** Evaluate satisfaction with waterbirth in adult low-risk laboring women randomized to waterbirth in comparison to women randomized to birth on land.

**Hypothesis 3.** Women in the waterbirth cohort will experience greater satisfaction scores on the revised United States Birth Satisfaction Scale-Revised (US-BSS-R), than women in the land cohort.

**Specific Aim 4:** Evaluate the safety of waterbirth for term low-risk neonates in comparison to land birth term low-risk neonates.

**Hypothesis 4a.** Infants in the waterbirth group will not experience more adverse outcomes (e.g., NICU admission, APGAR scores <7, umbilical cord injury, etc.) than infants born to women in the land cohort.

**Hypothesis 4b.** Infants in the waterbirth group will experience fewer instrumental (e.g., forceps, vacuum, etc.) or cesarean deliveries.

**Hypothesis 4c.** Infants born to women in the waterbirth cohort will have immediate skin-to-skin contact.

### III. STUDY POPULATION

The study participants will be healthy, low-risk, adult women seeking prenatal care with the Aurora UW faculty midwives and obstetricians at Aurora Sinai Medical Center. This will be a convenience sample of patients who voluntarily present for routine prenatal care, agree to study participation, and are randomized to either waterbirth or conventional land birth. As further research is needed to truly determine our desired sample size for testing our proposed hypotheses, our study aims to determine the feasibility of exploring or testing these hypotheses. This may allow us to make estimations for sample size to plan a larger, randomized controlled study in the future, or to contribute to meta-analyses of waterbirth.

Inclusion criteria based on *A model practice template for hydrotherapy in labor and birth (2016)*:

1. **Prenatal** low-risk, healthy, adult women ( $\geq 18$  years of age), including:
  - a. Able to speak and understand English
  - b. Women with a singleton gestation
  - c. Able to ambulate with no mobility restrictions (i.e., no difficulty getting from seated to standing)
  - d. Less than class III obesity (BMI  $< 40$  kg/m^2) at initiation of prenatal care
  - e. No active infections such as HIV, Hepatitis B, Hepatitis C, HSV outbreak (on prophylaxis acceptable),
    - i. GBS positive is acceptable
  - f. No pre-existing medical conditions such as: heart disease, uncontrolled asthma, diabetes, chronic hypertension, or other condition that requires continuous observation and/or activity restrictions
  - g. No high-risk pregnancy conditions: including preeclampsia, gestational hypertension, preterm gestation, multiple gestation, substance abuse, placental abruption or other unexplained vaginal bleeding, previous cesarean section,

suspected fetal macrosomia (>4500 gm) or intrauterine growth restrictions (<10th percentile), or other condition that requires continuous observation and/or activity restrictions per provider discretion; ultimately patient participation is dependent on provider recommendation

2. **Labor** inclusion criteria:

- h. Greater than 37 weeks and less than 42 completed weeks gestation in vertex presentation
- i. Not hypertensive or febrile (two blood pressures 140/90 four hours apart; two fevers of over 100.4 one hour apart)
- j. Category 1 fetal heart tones (obtained on a 20-minute admission external fetal monitor strip)
- k. Amniotic sac may be intact or ruptured. If ruptured, amniotic fluid must be clear.

Women will be **excluded** from the study if they do not meet the above inclusion criteria, or they will be further **excluded** under the following circumstances:

- 1. Known need for cesarean section
- 2. Participant may be excluded from the study at any time at the discretion of the birth attendant (reason for study exclusion will be documented but will remain in the study group previously selected based on intention to treat).

Women will be notified of exclusion by their provider, who will also notify appropriate study team members including coordinators. Documentation of exclusion will be done in Epic through a dotphrase (.waterbirthexclusion; Appendix A).

#### IV. STUDY DESIGN

This study is a pilot randomized control trial that aims to assess feasibility and explore or test (if possible) outcomes of waterbirth to that of conventional land birth for low-risk healthy women and neonates in a hospital setting in Milwaukee, WI. Low-risk healthy adult women will be enrolled from January 2022 through December 2025. The study could be introduced to potentially eligible women in their second trimester. Patient recruitment materials will also be placed in the waiting room and exam rooms. Patient recruitment materials will be created upon receipt of the birthing tub (October 2021) and will be approved by the IRB prior to use. We have attached the recruitment poster for approval.

We plan to enroll women using a random allocation rule in the ratio 2:1, with two women randomized to the waterbirth group for every one woman randomized to the land birth group. Women will be randomized in the Midwifery and Wellness Clinic, Exclusively for Women, and the Women's Health Clinic at Aurora Sinai Medical Center at the beginning of the third trimester (25 weeks 0 days to 34 weeks 0 days gestation) upon consent by the research coordinator, faculty physician(s), or midwives listed on this study. Consent will be documented with a dotphrase (.waterbirthconsent2; Appendix A). Patients will be presented with a sealed envelope which will contain a slip of paper identifying the patient's random assignment to either the waterbirth or land birth (again with a 2:1 randomization allocation). Currently, randomization is completed through REDcap.

We initially aimed to enroll 120 patients in the study, 80 enrolled within the waterbirth group and 40 in the land group. We recognize that some women will risk-out or opt-out because of the unpredictability of labor and birth. Additionally, we aim to approach most patients eligible for waterbirth with the understanding that some women will not want to participate in a research study. We have recalculated our sample sized based on the current enrollment attrition rate of 39.4% (rate in which patients risk out of the study). With a 2:1 allocation ratio, approximately 120 subjects were initially earmarked to be recruited into the study given 74 would be needed in the waterbirth and 37 would be needed in the land birth group to detect a 40% reduction in epidural use. Following the recommendations of Sakpal, we used the attrition rate (rate in which patients risk out of the study) to calculate adjusted sample sizes as 124 in the waterbirth group and 62 in the land birth group for a total of 186.

Participants who are ineligible for waterbirth will be excluded from both the land or water groups, and no further data will be collected. Please note that given the variable nature of birth, once a woman is randomized and enrolled to either group and meets ongoing eligibility criteria, an intention to treat model will be used for analysis following the birth.

Study participation will be offered to women seeking routine prenatal care in the Midwifery and Wellness Clinic, Exclusively for Women, and the Women's Health Clinic at Aurora Sinai Medical Center at the beginning of the third trimester (25 weeks 0 days to 34 weeks 0 days gestation). Eligible patients will be consented by a research study coordinator (risks and benefits will be done by an Aurora UW Medical Group midwifery or obstetric provider [CNM or physician] listed on this protocol) following the patient's prenatal visit. Note, in rare cases midwifery or obstetric providers listed on this protocol may conduct full consent. Following voluntary consent, all study participants will be randomized (see above for randomization).

Data collection will be completed as described below and will be obtained from Epic and the AUWMG midwifery database. A validated questionnaire *The US Birth Satisfaction Scale Revised* (US-BSS-R) will be used to evaluate maternal satisfaction and will be obtained within the first three days postpartum by either a study coordinator or midwife provider via an iPad. In some cases, the US-BSS-R will be collected by phone. We have obtained permission from the authors to use the validated scale US-BSS-R. The US-BSS-R is the recommended birth satisfaction measure by the International Consortium for Health Outcomes Measurement (ICHOM). Questions (below) are measured on 5-point Likert scale [strongly agree-strongly disagree] and a full copy of the scale was obtained from the authors and is available upon request:

1. I came through childbirth virtually unharmed.
2. I thought my labor was excessively long.
3. The delivery room staff encouraged me to make decisions about how I wanted my birth to progress.
4. I felt very anxious during my labor and birth.
5. I felt well supported by staff during my labor and birth.
6. The staff communicated well with me during labor.
7. I found giving birth a distressing experience.
8. I felt out of control during my birth experience.

9. I was not distressed at all during labor.
10. The delivery room was clean and hygienic

Routine management of the tub will be done in compliance with Infection Control and facility services. Water temperature will be maintained at less than or equal to 100 degrees Fahrenheit and will be monitored and recorded hourly through both a paper copy that will go the mid-wife call room (or study binder), as well as through an EPIC smart phrase .waterbirthlaborprogressnote (Appendix A and Appendix B). The Water Tub Protocol (Appendix C) has been created following receipt of the tub.

Waterbirths are an alternative method of pain control and are not standard of care. Therefore, only patients who voluntarily agree to participate in this study will be able to undergo waterbirth. We will collect regularly recorded measures, in addition to patient satisfaction surveys for all participants. The US-BSS-R questionnaire is the only deviations from standard care for patients in the conventional land birth group.

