## VII. STATISTICAL PLAN

The **primary outcome** we seek is a reduction of IV narcotic and epidural anesthesia use. We anticipate that this pilot project would be powered to detect a very clinically meaningful percentage point reduction in use of IV narcotic and epidural anesthesia. We carried out a power analysis using G\*Power 3.1.9.6. Using the Fleiss methodology to estimate power calculations with 80% power at the 0.05 level of significance, we estimate the following: to detect about 80% reduction in IV narcotic use from 24.5% down to 5.5%, estimated need would be 68 in the waterbirth group, 34 in the control group. To detect about 40% reduction in epidural use from 59% down to 34%, estimated need would be 74 in the waterbirth group, 37 in the control group. We have recalculated our sample sized based on the current enrollment attrition rate of 39.4%

(rate in which patients risk out of the study). With a 2:1 allocation ratio, approximately 120 subjects were initially earmarked to be recruited into the study given 74 would be needed in the waterbirth group and 37 would be needed in the land birth group to detect a 40% reduction in epidural use. Following the recommendations of Sakpal, we used the attrition rate (rate in which patients risk out of the study) to calculate adjusted sample sizes as 124 in the waterbirth group and 62 in the land birth group for a total of 186. We continue to approach most pregnant people eligible for waterbirth with the understanding that some will not want to participate in a research study. The results of this pilot should inform sample size required for a larger, definitive study that would be powered to detect smaller, still meaningful reductions in narcotic/epidural use.

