## **VII. DATA COLLECTION**

- » From January 2022 through December 2025 eligible women will be offered study participation during routine prenatal care at 25 weeks 0 days to 34 weeks 0 days gestation. The study could be introduced to potentially eligible women in their second trimester. Several data elements will be reviewed and collected from the delivery record in Epic and the AUWMG midwifery database. REDCap will be utilized for data collection and storage for this study. Data collection will be completed by those listed on this study. After the first year of data collection, we plan to conduct an interim analysis and present year one preliminary data at a scientific meeting (Advocate Aurora Scientific Day 2023).

Variables to be collected at time of consent after coordinators have discussed participating in a randomized control trial:

- Do you wish to voluntarily participate in our randomized control trial that aims to evaluate maternal/neonatal outcomes associated with waterbirths, as well as your satisfaction with the birthing process? (0=No; 1=Yes)

Variables to be collected:

1. *Study related variables*
  - a. Medical reason/s participant becomes ineligible for waterbirth
    - i. Hep C positive (0=No; 1=Yes)
    - ii. Gestational age <37 or >42
    - iii. Non-vertex presentation (0=No; 1=Yes)
    - iv. Hypertensive (0=No; 1=Yes)
    - v. Febrile (0=No; 1=Yes)
    - vi. Category 2 or 3 fetal heart tones (0=No; 1=Yes)
    - vii. Amniotic sac is ruptured and fluid is not clear (0=No; 1=Yes)
    - viii. Other: notes
  - b. Maternal decision to withdraw participation (i.e. desire to leave the water): notes
2. *Maternal variables*
  - a. REDCap Record ID
  - b. Medical record number
  - c. Date of birth
  - d. BMI (kg/m^2) at initiation of prenatal care
    - a. Height (inches) and weight (lbs) at initiation of prenatal care
  - e. Race
  - f. Ethnicity
  - g. Education level
  - h. Marital status
  - i. Gravidity
  - j. Paritya
  - k. Date and time of admission
  - l. Date and time of delivery
  - m. Gestational age at time of delivery (WxDx)
  - n. Maternal position for birth:
    - a. upright (0=No; 1=Yes)
    - b. squatting (0=No; 1=Yes)
    - c. semi-sitting (0=No; 1=Yes)
    - d. left tilt (0=No; 1=Yes)
    - e. right tilt (0=No; 1=Yes)
    - f. hands and knees (0=No; 1=Yes)
    - g. standing (0=No; 1=Yes)
    - h. other (0=No; 1=Yes)
      - i. describe

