  - o. Quantified blood loss (QBL calculation begins after the delivery of the placenta using the blue bag; clots, linens, and lap sponges will be weighed. Unit protocol will be followed. Hemorrhage QBL  $\geq$  1,000 mL)
  - p. Was patient switched from waterbirth to land birth?
    - a. Why?

- q. Was patient switched from any birth to cesarean or operative delivery?
    - a. Why?
    - b. Cesarean (0=No; 1=Yes)
    - c. Instrumental delivery (0=No; 1=Yes)
      - i. Forceps (0=No; 1=Yes)
      - ii. Vacuum (0=No; 1=Yes)
  - r. Labor duration and time (by phase: first, second, third)
    - a. Induction (0=No; 1=Yes)
    - b. Spontaneous labor (0=No; 1=Yes)
  - s. Dilation at time of admission of birth
  - t. Medications used (analgesia and anesthesia) (0=No; 1=Yes)
    - a. Epidural (0=No; 1=Yes)
      - i. Epidural eligibility (0=No; 1=Yes)
    - b. Spinal epidural (0=No; 1=Yes)
    - c. IV narcotic medication (Nubain or Stadol) (0=No; 1=Yes)
  - u. Maternal complications (0=No; 1=Yes)
    - a. Laceration (1st, 2nd, 3rd, 4th degree)
      - i. Episiotomy (0=No; 1=Yes)
    - b. Shoulder dystocia (0=No; 1=Yes)
  - v. Maternal satisfaction (US-BSS-R, modified)
    - a. Postpartum day survey was completed (0=PPD0; 1=PPD1; 2=PPD2; 3=PPD3)
  - w. Was breastfeeding initiated at any point prior to discharge? (0=No; 1=Yes)
  - x. Date and time of discharge
    - a. Length of hospital stay
3. *Newborn variables*
- a. Date and time of skin-to-skin contact
    - a. Time from birth to skin-to-skin contact
  - b. One- and five-minute APGAR scores
  - c. Were there any newborn complications at time of birth? (0=No; 1=Yes)
    - a. If yes, newborn complications including:
      - i. NICU admission (0=No; 1=Yes)
        - 1. If yes, NICU admission and discharge date for LOS
      - ii. Infection (0=No; 1=Yes)
      - iii. Injury (0=No; 1=Yes)
      - iv. Cord injury (0=No; 1=Yes)
      - v. Other (0=No; 1=Yes)
        - 1. What?
  - d. If available, Cord Ph (arterial and venous)
  - e. At approximately 4-8 weeks postpartum, coordinator follow-up regarding newborn status (at postpartum visit or via phone call, etc.)
    - a. Were we able to touch base (0=No; 1=Yes)
    - b. If yes, were there any neonatal complications since discharge? (0=No; 1=Yes)
    - c. If any complications since discharge?
      - i. Neonatal hospital admission (0=No; 1=Yes)
        - 1. If yes, follow-up comments

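### Women who opt out or deliver elsewhere have no defined data field in the land arm, no stated route to their epidural and IV narcotic outcome, and no allowance in the target of 186

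*Combined protocol and SAP*

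**What the plan says.** Women are randomized at 25 weeks 0 days to 34 weeks 0 days, upon consent, and learn their arm then (IV. Study Design). The same section states that "only patients who voluntarily agree to participate in this study will be able to undergo waterbirth", so a land assignment rules out waterbirth at this hospital.

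Section IV expects voluntary losses as well as medical ones: "We recognize that some women will risk-out or opt-out because of the unpredictability of labor and birth". The sample size uses a "current enrollment attrition rate of 39.4" percent, and both section IV and VII. Statistical Plan define that figure as risk-outs: "we used the attrition rate (rate in which patients risk out of the study) to calculate adjusted sample sizes". The result is "124 in the waterbirth group and 62 in the land birth group for a total of 186".

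In VII. Data Collection, the single withdrawal item (study-related variables, 1b) reads "Maternal decision to withdraw participation (i.e. desire to leave the water): notes". The crossover item (maternal variables, p) runs one way: "Was patient switched from waterbirth to land birth". On sources, the section says "Several data elements will be reviewed and collected from the delivery record in Epic and the AUWMG midwifery database"; section IV names the same two sources. A follow-up contact at about 4-8 weeks postpartum is listed under newborn variables and asks only about the newborn.

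Section IV also promises an intention-to-treat analysis for randomized women who continue to meet eligibility criteria. It does not say how a missing outcome is handled.

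**The concern.** Roughly 3 to 17 weeks pass between an open assignment and a term birth (34 to 37 weeks at the shortest, 25 to 42 at the longest). In that time a land-assigned woman who wanted waterbirth has a reason to leave that a water-assigned woman lacks. If she withdraws or gives birth elsewhere, item 1b does not fit her, the crossover item does not apply, and the plan describes no way to learn whether she had an epidural or IV narcotic. Water-assigned women who leave before labor are no better covered.

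Two things are at stake. If departure differs by arm and leavers differ from stayers in analgesia use, the primary comparison is biased, and intention to treat cannot correct for outcomes that were never obtained. In addition, this is a pilot meant to judge the feasibility of a multi-site trial. Retention by arm after an open third-trimester assignment is one of the results that trial will need, and the listed variables do not capture it in a usable form. A smaller, separate matter is that the sample size has almost no reserve for voluntary loss.

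**Working it through.** **Inputs from the documents.** Epidural 59% (control) and 34% (waterbirth); 74 and 37 evaluable; 80% power at 0.05 (VII. Statistical Plan). One-tailed p below 0.05 (same section). Risk-out rate 39.4% and target 124 + 62 = 186 (IV. Study Design). **Not in the documents:** an opt-out rate, the share leaving each arm, and leavers' epidural use. These are assumed below and varied.

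**1. The plan's own figures.** The Fleiss formula with pooled variance, one-sided 0.05, 80% power, 2:1 allocation and no continuity correction gives 36 land and 72 waterbirth, against the stated 37 and 74. That is close enough to count as reproduced. The inflation is n/(1 − 0.394):
- waterbirth 74/0.606 = 122.1, rounded up to 123
- land 37/0.606 = 61.06, rounded up to 62

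The stated 124 is 2 × 62, which keeps the ratio and gives 186.

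**2. Reserve for opt-outs.** 124 × 0.606 = 75.1 and 62 × 0.606 = 37.6, together 112.7. The requirement is 74 + 37 = 111, so the reserve is 1.7 women.

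**3. Power if some still-eligible women opt out.** Power is by exact enumeration of the one-tailed Pearson test at 59% against 34%.

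| Opt-out among women still eligible (assumed) | Waterbirth | Land | Power |
|---|---|---|---|
| 5% | 75.1 × 0.95 = 71.4, about 71 | 37.6 × 0.95 = 35.7, about 36 | 80.1% |
| 10% | 75.1 × 0.90 = 67.6, about 68 | 37.6 × 0.90 = 33.8, about 34 | 78.7% |

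The denominator matters. If 5% or 10% of all randomized women is instead added to the 39.4%, then 186 × 0.556 = 103.4 or 186 × 0.506 = 94.1 remain. With whole numbers at 2:1 that is about 68/34 or 62/31, and power is 78.7% or 74.9%.

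**4. Bias if land-assigned women leave.** Let a share w of land women leave, with epidural rate q, when the true land rate is 59%. The observed land rate is (0.59 − w × q)/(1 − w). Take w = 10%, which leaves 37 × 0.90 = 33.3, about 33 land women, against 74 waterbirth women. Suppose there is no true effect (59% in both arms) and no loss from the water arm. With no loss at all (37/74), the exact one-tailed false-positive rate is 4.8%.

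| Leavers' epidural rate q (assumed) | Observed land rate | False-positive rate |
|---|---|---|
| 20% | 0.570/0.90 = 63.3% | 10.6% |
| 34% (the plan's waterbirth rate) | 0.556/0.90 = 61.8% | 8.1% |
| 59% (the plan's control rate) | 0.531/0.90 = 59.0% | 4.8% |
| 80% | 0.510/0.90 = 56.7% | 3.0% |

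Rounding to 34 and 75 women instead changes these rates by less than one percentage point. The sign of the bias depends on q: toward waterbirth below 59%, none at 59%, and against waterbirth above it.

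**The case against.** A reader might infer that land-assigned women who leave drop out of the trial uncounted, and that the epidural comparison is therefore tilted toward waterbirth. The documents support neither step.

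*Uncounted.* Randomization is done in REDCap, each woman has a REDCap record, and consent is charted. The number randomized minus the number analysed can be obtained for each arm. Item 1b opens with a general reference to withdrawing participation and takes free text, so a land withdrawal could be entered there. What is missing is a defined field and a route to the outcome.

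*Tilted toward waterbirth.* This needs land leavers to use fewer epidurals than stayers. Nothing in the documents says so, and the table shows the sign reversing. The sentence that expects opt-outs attributes them to the unpredictability of labor, not to disappointment with assignment. Nor do the documents say that waterbirth can be had nearby. The motive is an inference from the rule that waterbirth is confined to the trial.

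Other points on that side carry weight. The power loss is small for a study that will test its hypotheses only if sample size permits. Intention to treat is stated for women who stay eligible, and women excluded at the birth attendant's discretion are kept in their assigned group. How far Epic reaches beyond this hospital is not stated. The consent pages are not in the file, so withdrawal terms there cannot be called absent.

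These points reduce the size of the concern but do not remove it. None of them supplies the primary outcome for a woman who gives birth outside the two named sources.

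**Conclusion.** The concern holds as a gap in capturing voluntary loss and in obtaining its outcomes. It does not show that bias exists. The plan expects opt-outs, but its only withdrawal item is explained in terms that cannot apply to the land arm, and it describes no route to the analgesia outcome of women who deliver elsewhere. Differential loss could push the comparison either way. It would favor waterbirth if land leavers are those most set on avoiding analgesia, which is plausible here but undocumented.

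At an assumed 10% land-arm departure, the one-tailed false-positive rate runs from 3.0% to 10.6% across assumed leaver epidural rates of 80% down to 20%. The calculation takes no true effect and no loss from the water arm.

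The sample-size part is minor. The 186 covers risk-outs almost exactly and nothing more, but opt-out of 5% among women still eligible leaves power at about 80%, and 10% costs less than two points against the 80% target. The possible bias is the stronger reason to act, and the remedy is cheap.

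**What to change.** 1. In VII. Data Collection, replace item 1b with a coded opt-out and transfer item for both arms: date, assigned arm, reason, and birth elsewhere (yes/no). Record leaving the water as a separate item.
2. For women who leave but permit contact, ask about epidural and IV narcotic use at the existing 4-8 week contact, and analyse them in their assigned arm.
3. Report opt-outs by arm, with the numbers randomized and analysed.
4. In IV. Study Design and VII. Statistical Plan, restate the evaluable numbers and power for all-cause loss instead of risk-outs alone, and name the denominator of the opt-out rate. This does not require enrolling more women.

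The cost is one revised REDCap item, one question at a contact already planned, and a few sentences of text. The downside is that the outcome is self-reported for a few women and the stated power is slightly lower. Clinical management is unchanged.
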